5.3.3.2 Definition of Disease Progression

Disease progression according to 2008 Modified IWCLL NCI-WG Criteria for Tumor Response is characterized by at least one of the following:

- Appearance of any new lesion, such as enlarged lymph nodes (> 1.5 cm), splenomegaly, hepatomegaly, or other organ infiltrates. An increase by 50% or more in greatest determined diameter of any previous site.
- An increase in the previously noted enlargement of the liver or spleen by 50% or more or the de novo appearance of hepatomegaly or splenomegaly.
- An increase in the number of blood lymphocytes by 50% or more with at least 5,000 B lymphocytes per microliter. The increase should be assessed against the best response while on study.
- Transformation to a more aggressive histology (e.g., Richter's Syndrome). Whenever possible, this diagnosis should be confirmed by lymph node biopsy. For subjects experiencing disease progression due to Richter's Syndrome while on study, supplemental data may be collected.
- Occurrence of cytopenia (neutropenia, anemia or thrombocytopenia) attributable to CLL.

5.3.4 Safety Variables

The following safety evaluations will be performed during the study: serious adverse event and adverse event monitoring including AEs of special interest (Section 6.1.1.4), vital signs, physical examination, and laboratory assessments. Certain types of events require immediate reporting to the Sponsor, as outlined in Section 6.1.5. Safety will be monitored on an ongoing basis and summarize periodically in aggregate safety reports and end of study.

5.3.5 Pharmacokinetic Variables

Values for the PK parameters of venetoclax, including the apparent clearance (CL/F), will be determined using a population PK modeling approach. Additional parameters may be calculated if useful in the interpretation of the data.

5.3.6 Biomarker Variables

Biomarker Research Variables

Peripheral blood and/or bone marrow biospecimens will be collected to conduct exploratory analyses to investigate biomarkers. The types of biomarkers to be analyzed may include, but are not limited to, nucleic acids, proteins, lipids or metabolites. Cells isolated from the peripheral blood/bone marrow may be analyzed to assess specific genetic mutations within the tumor cells, or to track the tumor cells to determine the presence of minimal residual disease. Additionally, the expression levels (RNA or protein) of molecules involved in controlling the apoptosis machinery, including but not limited to BCL-2 family members, may also be correlated with efficacy.

Evaluations may include analyzing biomarkers related to the pathway(s) targeted by the study drug or those believed to be related to the disease or to drug response. The information learned from analyzing these samples may be used to investigate factors influencing response to treatment, scientific questions related to CLL, and/or in the development of new therapies and diagnostic tests. The results of biomarker testing may not be included with the study summary.

5.3.7 Health Economic and Patient-Reported Outcome Measures

5.3.7.1 Functional Assessment of Cancer Therapy – Leukemia (FACT-Leu) Questionnaire

The FACT-Leu is a 44-item, leukemia-specific questionnaire designed to assess subject health-related quality of life (HRQoL) and leukemia-specific symptoms using a 'core' set of questions (Functional Assessment of Cancer Therapy-General; FACT-G), as well as a cancer site-specific leukemia subscale.³⁴ The FACT-G is a 27-item compilation of general questions scored on a 5-point scale ranging from 0 = "not at all" to 4 = "very much."³⁵ The items are divided into 4 primary HRQOL domains: Physical Well-being (7 items; score range, 0 – 28), Social/Family Well-being (7 items; score range, 0 – 28), Emotional Well-being (6 items; score range, 0 – 24), Functional Well-being (7 items; score range, 0 – 28).³⁶

The leukemia-specific subscale consists of 17 items (score range, 0 – 68) that assess subject concerns relating to leukemia. Three summary scales: FACT-Trial Outcome Index (score range, 0 – 124) a summary scale composed of the Physical Well-being, Functional Well-being, and leukemia-specific subscales; FACT-G (score range, 0 – 108) and the FACT-Leukemia Total (score range, 0 – 176) can also be calculated. Higher scores are reflective of better HRQOL. Minimally important differences (MIDs) have been identified for the different FACT-Leu scales: Physical Well-being, 2 – 3 points; Social/Family Well-being, not available; Emotional Well-being, 2 points; Functional Well-being, 2 – 3 points; FACT-G, 3 – 7 points; Leukemia-specific subscale, 4 – 7 points; FACT-Trial Outcome Index, 5 – 6 points; and FACT-Leukemia Total, 6 – 12 points.

Scores will be summarized descriptively at each assessment. The impact of treatment on quality of life over time will be assessed by calculating the change in scores from baseline at each assessment time point. Scores will be calculated according to the FACT-Leu scoring manual.

5.3.7.2 Functional Assessment of Chronic Illness Therapy – Fatigue (FACIT-F) Scale

The FACIT-F measures fatigue and its effect on functioning and daily activities.³⁷ The FACIT-F has 13 items answered on a 5-point rating scale based on a 7-day recall period. Scores range from 0 to 52, with lower scores reflecting greater fatigue. The instrument has shown good reliability and validity based on analyses of the general population in the United States, subjects with cancer, and subjects with rheumatoid arthritis.³⁷⁻³⁹ The MID of the FACIT-F scale has been determined to be 3 points.⁴⁰

Scores will be summarized descriptively at each assessment. The impact of treatment on fatigue over time will be assessed by calculating the change in score from baseline at each assessment time point. Scores will be calculated according to the FACIT-F scoring manual.

5.3.7.3 EuroQol 5 Dimensions (EQ-5D-5L)

The EuroQol 5 Dimensions (EQ-5D-5L) is a generic preference instrument that has been validated in numerous populations.^{41,42} The EQ-5D-5L has five dimensions: mobility, self-care, usual activities, pain/discomfort and anxiety/depression. These dimensions are measured on a five level scale: no problems, slight problems, moderate problems, severe problems, and extreme problems. The scores for the 5 dimensions are used to compute a single utility index score ranging from zero (0.0) to 1 (1.0) representing the general health status of the individual. The EQ-5D-5L also contains a visual analog scale (VAS) to assess the subject's overall health. The MID for the EQ-5D utility index score in cancer subjects is 0.08, and the MID for EQ-5D VAS is 7.^{43,44}

Each of the five dimensions of the EQ-5D-5L, the VAS and overall utility score will be calculated using the EuroQol scoring manual, and summarized (mean, std. dev., median) at each assessment. The impact of treatment over time will be assessed by calculating the change in score from baseline at each assessment time point.

5.4 Removal of Subjects from Therapy or Assessment

5.4.1 Discontinuation of Individual Subjects

Each subject has the right to withdraw from the study and/or study drug treatment at any time. In addition, the investigator may discontinue a subject from study drug treatment at any time if the investigator considers it necessary for any reason including:

- The investigator believes it is in the best interest of the subject
- Subject's response to therapy is unsatisfactory, as evidenced by progression of disease while on study drug
- The subject requires other cancer treatment (e.g., radiotherapy, cancer-related surgery as a result of tumor progression, alternate anti-neoplastic agents) during the study period
- unacceptable toxicity
- The subject becomes pregnant while on the study

- drug/protocol non-compliance

The investigator will inform AbbVie prior to discontinuing a subject from the study by contacting the Clinical Team Leader as identified in Section 7.0. All subjects will be included for analysis of safety data. Subjects who withdraw from the study will not be replaced unless they are not evaluable.

Subjects will continue to be followed for unresolved AEs and survival information for any subject who has not experienced PD at the time of venetoclax discontinuation.

Final Visit

Upon study drug discontinuation and/or upon discontinuation from the study, the reason(s) for discontinuation will be recorded in electronic case report forms (eCRFs) and a final visit will be performed. The final visit procedures as listed in [Appendix D](#) should be performed as soon as possible after discontinuation from study drug.

30-Day Safety Follow-Up Visit

A 30-Day Safety Follow-up Visit should be performed approximately 30 days (\pm 3 days) following the last dose of venetoclax. The 30 day safety follow up procedures listed in [Appendix D](#) should be performed.

Post Treatment and Survival Follow-Up Calls

For subjects who discontinue venetoclax therapy, but do not discontinue the study, post treatment follow-up calls will be performed every 6 months (\pm 7 days) for survival information (i.e., disease progression, the date and cause of death, post-treatment cancer therapies, etc.) and will be collected via telephone calls for a period of 2 years and recorded in the eCRFs.

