After treatment discontinuation, subjects will be followed for disease progression (if progression has not already occurred) and survival. Post-treatment calls will be performed every 6 months until discontinuation from the study. Survival information (i.e., the date and cause of death, post-treatment cancer therapies, date of progression, etc.) will be collected. This period will continue for two years following discontinuation of venetoclax.

All study procedures will be performed as outlined in Section 5.3.1.1 and [Appendix D](#) and [Appendix E](#).

For subjects who continue to derive benefit after 2 years of treatment, AbbVie will work with the investigator on a case by case basis to consider the potential continuation of venetoclax therapy. In countries where venetoclax is commercially available, extension of therapy may not be allowed.

A safety analysis will be performed for all subjects participating in the study who took at least one dose of study drug. For the study as a whole, serious adverse events and adverse events will be evaluated and summarized. Laboratory test results and vital signs will be explored for trends and summarized.

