For any subject who has not experienced progressive disease (PD) at the time of permanent discontinuation of venetoclax, follow-up phone calls will continue until death, discontinuation from the study or upon study completion.

Response criteria definitions are outlined in 2008 Modified IWCLL-WG Criteria for Tumor Response. See [Table 5](#).

For patients with only Partial Remission at Week 48 an additional CT and a bone marrow examination can be done between Week 48 and Week 108 to confirm CR if there is a possibility that a patient is in Complete Remission based on laboratory tests and a disease assessment physical examination.

NOTE: Disease assessments may be performed approximately 7 days prior to the scheduled visit.

Computed Tomography Scans (or Magnetic Resonance Imaging)

A CT scan with contrast will be accepted if previously performed within 35 days prior to the first dose of venetoclax. Otherwise, a CT scan must be performed within the Screening window (28 days) for all subjects. A CT scan will be performed for all subjects at Week 48 to confirm disease response. Contrast-enhanced CT scans including neck, chest, abdomen, and pelvis will be performed to assess response to treatment. A contrast-enhanced MRI of the neck, chest, abdomen and pelvis with a non-contrast CT scan of the chest may be used for subjects in whom a contrast CT is medically contraindicated (i.e., subjects with a severe allergy to CT contrast agents or subjects with impaired renal clearance). Whichever method is used at Screening should be consistently used throughout the duration of the study.

Any CT scan (or MRI) performed as standard of care throughout the study should be captured on the eCRF.

NOTE: CT scans (or MRI) may be performed 7 days prior to the scheduled visit.

Bone Marrow Aspirate and Biopsy

At baseline, a bone marrow aspirate and biopsy are not required; however results should be recorded if available. If the subject achieves a CR by clinical criteria and confirmatory CT scan, a bone marrow aspirate and biopsy will be performed to confirm the CR. Whenever possible the bone marrow aspirate for biomarker MRD assessment should be split from this sample. If a CT scan is performed and does not confirm a CR, a bone marrow biopsy should not be obtained.

Bone marrow aspirates and biopsies performed as standard of care throughout the study should also be captured on an eCRF.

Subject Calendars/Diaries

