After treatment discontinuation, subjects will be followed for disease progression (if progression has not already occurred) and survival. Post-treatment calls will be performed every 6 months until discontinuation from the study. Survival information (i.e., the date and cause of death, post-treatment cancer therapies, date of progression etc.) will be collected. This period will continue for 2 years following discontinuation of venetoclax.

Extended Access Phase

In countries where venetoclax is not commercially available, subjects who continue to derive benefit after 2 years of treatment may be able to extend their treatment for up to 2 additional years. If a subject in the extended access phase of this study continues to derive benefit from Venetoclax after the 2-year extension, then per PI's assessment, subjects who are transferring to the venetoclax extension study, Study M19-388, may remain in Extended Access for up to additional 1 year or until the extension study is approved and initiated at the site, whichever is sooner. AbbVie will work with the

investigator on a case by case basis to consider the potential continuation of venetoclax therapy. The Extended Access Visits will include:

- Collection of Survival information
- AE/SAE/Con Med assessment
- Study drug reconciliation and dispensing

All other procedures should be performed as standard of care. The specific study assessments to be performed during these visits are detailed in [Appendix E Study Activities](#).

Assignment of Subject Numbers

Subjects will be assigned unique consecutive subject numbers at screening, as described in Section 5.5.3. The results of all screening evaluations must be within clinically acceptable limits, upon review by the investigator before a subject can be administered study drug. Subjects will not be enrolled in the study if laboratory or other screening results are unacceptable.

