6.1.1 Definitions

6.1.1.1 Adverse Event

An adverse event (AE) is defined as any untoward medical occurrence in a subject or clinical investigation subject administered a pharmaceutical product and which does not necessarily have a causal relationship with this treatment. An adverse event can therefore be any unfavorable and unintended sign (including an abnormal laboratory finding), symptom, or disease temporally associated with the use of a medicinal (investigational) product, whether or not the event is considered causally related to the use of the product.

Such an event can result from use of the drug as stipulated in the protocol or labeling, as well as from accidental or intentional overdose, drug abuse, or drug withdrawal. Any worsening of a pre-existing condition or illness is considered an adverse event.

Worsening in severity of a reported adverse event should be reported as a new adverse event. Laboratory abnormalities and changes in vital signs are considered to be adverse events only if they result in discontinuation from the study, necessitate therapeutic medical intervention, meets protocol specific criteria (see Section 6.1.8 Toxicity Management) or if the investigator considers them to be adverse events.

For this protocol, disease progression is an efficacy endpoint. These data will be captured as efficacy assessment data only. Thus, events that are clearly consistent with the expected pattern of progression of the underlying disease (such as transformation to more aggressive histology) will result in discontinuation from the study and should not be recorded as adverse events but reported on the Study Completion eCRF. However, if a subject experiences an adverse event (e.g., pneumonia, pyrexia, fatigue, etc.) and is also found to have disease progression, report the adverse event. If there is any uncertainty as to whether an event is due to disease progression, it should be reported as an adverse event.

An elective surgery/procedure scheduled to occur during a study will not be considered an adverse event if the surgery/procedure is being performed for a pre-existing condition and the surgery/procedure has been pre-planned prior to study entry. However, if the pre-existing condition deteriorates unexpectedly during the study (e.g., surgery performed earlier than planned), then the deterioration of the condition for which the elective surgery/procedure is being done, will be considered an adverse event.

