- s. The Quality of Life Questionnaires should be administered and completed prior to any other study procedures being performed at these visits. Refer to Section 5.3.7, Health Economic and Patient-Reported Outcome Measures, for further information.
- t. 30-Day Safety Follow-up visit should occur approximately 30 days (\pm 3 days) after the last dose of venetoclax.
- u. Upon discontinuation of study drug treatment, survival information (i.e., the date/cause of death, post treatment cancer therapies, etc.) will be collected every 6 months (\pm 7 days) for a period of 2 years.
- v. ECOG performance status may be performed within 72 hours before or after the scheduled visit starting with Week 24.
- w. Collect (immediately) prior to venetoclax dosing (0 hour) on Week 24 Day 1. The date and time (to the nearest minute) the venetoclax doses were taken, and whether or not the venetoclax doses were taken with a meal, will be recorded on the eCRF for the Week 24 Day 1 venetoclax PK day and for the 2 days prior to the Week 24 Day 1.
- x. Survival information includes i.e., the date/cause of death, post treatment cancer therapies, etc.

- y. In countries where venetoclax is not commercially available, subjects who continue to derive benefit after 2 years of treatment may be able to extend their treatment for up to 2 additional years. AbbVie will work with the investigator on a case by case basis to consider the potential continuation of venetoclax therapy. Subjects who participate in the 2 year Extended Access phase will have study drug assigned at Week 108. For patients that are not participating in the 2 year Extended Access phase, the Week 108 visit is the Final visit. The specific study assessments to be performed at the Extended Access visits are detailed in [Appendix E](#), Study Activities.

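### Protocol 5.4.1 and 6.1.1.1 conflict with the rest of the protocol on whether survival follow-up continues after progression; if some sites took the narrow reading, overall survival could be modestly overstated

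*Protocol*

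**What the plan says.** **Narrow wording.** Protocol 5.4.1 states that subjects continue to be "followed for unresolved AEs and survival information for any subject who has not experienced PD at the time of venetoclax discontinuation". Protocol 6.1.1.1 states that events clearly consistent with progression "will result in discontinuation from the study and should not be recorded as adverse events but reported on the Study Completion eCRF".

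**What progression ends.** In 5.4.1 progression is listed only as a reason to stop study drug: "response to therapy is unsatisfactory, as evidenced by progression of disease while on study drug". So 5.4.1 and 6.1.1.1 differ on whether progression ends treatment or participation.

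**Inclusive wording.** Protocol 5.3.1.1 (Post-Treatment and Survival Assessments) says: "After treatment discontinuation, subjects will be followed for disease progression (if progression has not already occurred) and survival". The Synopsis and 5.1 say the same, for 2 years. The bracketed condition limits progression follow-up, not survival follow-up. Appendix D footnote u says: "Upon discontinuation of study drug treatment, survival information (i.e., the date/cause of death, post treatment cancer therapies, etc.) will be collected every 6 months", for 2 years and with no progression condition. Appendix E footnote e matches it.

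**Limit on the calls.** Protocol 5.1 says: "Post-treatment calls will be performed every 6 months until discontinuation from the study". The Synopsis and 5.3.1.1 carry the same limit. In 5.4.1 the calls paragraph begins: "For subjects who discontinue venetoclax therapy, but do not discontinue the study, post treatment follow-up calls will be performed every 6 months".

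**Ambiguous wording.** Protocol 5.3.1.1 (Disease Assessments) says: "For any subject who has not experienced progressive disease (PD) at the time of permanent discontinuation of venetoclax, follow-up phone calls will continue". This may describe progression follow-up only, or all follow-up.

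**Analysis.** SAP 10.1.1 counts all deaths, on or off drug, and censors other subjects when last known alive. SAP 10.1 plans no efficacy testing.

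**The concern.** A site that takes 6.1.1.1 literally completes the study form for a progressor and records the subject as off study. The 6-monthly calls then stop, because 5.4.1 gives them only to subjects still in the study and the Synopsis, 5.1 and 5.3.1.1 run them only until study discontinuation. The last contact would be about the 30-Day Safety Visit, and SAP 10.1.1 would censor OS there.

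That censoring depends on progression. If subjects die faster after progression than before it, those removed from the risk set are those most likely to die, and the Kaplan-Meier curve sits too high. The SAP plans no OS sensitivity analysis for this. At stake is the accuracy of a secondary endpoint, not the primary complete remission rate.

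**Working it through.** **No stated figure to reproduce.** The documents give no OS rate, death count or hazard, so every rate below is an assumption.

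**Horizon.** SAP Table 1 has one cutoff with efficacy data, 30 April 2018. If it follows Protocol 8.1.3 (last subject at the Week 48 assessment), the shortest potential follow-up is nominal day 330 (SAP Table 2), or 330/30.4 = about 10.8 months. I therefore use 12-month OS.

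**Assumed inputs.**
- Exponential time to progression, median 24, 30 or 48 months; for 30, λp = ln 2/30 = 0.02310 per month.
- Death without progression, 6% by 24 months: λd = −ln(0.94)/24 = 0.00258.
- Median survival after progression 12, 24 or 36 months: λq = ln 2/12, /24, /36 = 0.0578, 0.0289, 0.0193.
- In a fraction f of subjects the narrow reading applies, and progressors are lost one month after progression.

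**Formulas.** With k = λp + λd:
- Alive without progression: P0(t) = exp(−kt).
- Alive after progression: P1(t) = λp/(k − λq) × [exp(−λq t) − exp(−kt)].
- True OS = P0 + P1.
- Progressors still observed: A(t) = (1 − f)·P1(t) + f·P1*(t), where P1* counts those alive within one month of progression.
- Kaplan-Meier limit = exp(−∫h), with h(t) = (λd·P0 + λq·A)/(P0 + A).

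**Example** (medians 30 and 12 months, t = 12): true OS = 0.7348 + 0.1691 = 0.9039. The Kaplan-Meier limit is 0.9154 for f = 0.25 and 0.9279 for f = 0.5, an overstatement of 1.2 and 2.4 points.

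**Results at 12 months**, for post-progression medians of 12/24/36 months:

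| Median time to progression | True OS, % | Overstatement, f = 0.25 (points) | Overstatement, f = 0.5 (points) |
|---|---|---|---|
| 24 months | 88.9/92.7/94.1 | 1.36/0.74/0.49 | 2.86/1.55/1.03 |
| 30 months | 90.4/93.5/94.7 | 1.16/0.63/0.41 | 2.40/1.30/0.86 |
| 48 months | 92.7/94.7/95.5 | 0.79/0.43/0.28 | 1.62/0.87/0.58 |

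With λq set equal to λd the overstatement is 0.

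**Which count would reveal the problem.** Counting subjects censored soon after progression does not work, because calls are 6-monthly. With 250 subjects, median time to progression 30 months, follow-up uniform over 11 to 22 months and drug stopped at progression, about 21 to 23 living progressors have progressed less than 6 months before the cutoff. Under perfect compliance they have had no call yet. The quarter scenario loses 17 to 18, so the two cannot be told apart. The 30-Day Safety Visit also runs from last dose, so a loss can fall outside 30 days of progression when drug stops later.

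Restricting the count to progressors whose first call was already due removes this overlap. Under full compliance the count is zero apart from ordinary loss and withdrawn consent. In the quarter scenario the mean of 1 − exp(−k(F − 6)) over follow-up F of 11 to 22 months is 0.234. The count is then 0.25 × 250 × (λp/k = 0.900) × 0.234 × exp(−λq) = about 12 to 13.

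**The case against.** The strongest reply is that the protocol, read as a whole, already answers the question.

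- The 5.4.1 sentence is loosely built and restricts only by implication. The calls paragraph in the same section has no progression condition.
- The Synopsis, 5.1, 5.3.1.1 and both footnotes are inclusive.
- SAP 10.1.1 counts deaths off drug and draws last-alive dates from survival visits and post-treatment therapy records.
- Protocol 6.1.1.1 tells sites where to record progression; it is not the section on discontinuation.
- The sentence under Disease Assessments can be read as progression follow-up only.

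Most of this stands: the inclusive reading is the apparent intent, and that limits the weight of the point. It does not remove the conflict. The Synopsis, 5.1, 5.3.1.1 and the 5.4.1 calls paragraph all stop at study discontinuation, so a site that closes out a progressor under 6.1.1.1 has, on the letter, complied with each of them. Only the two footnotes contradict it without that limit. Protocol 6.1.2.1.1, on CLL deaths during survival follow-up, fits either reading.

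A reader might infer that the plan censors OS at progression, or that deaths were missed. Neither is supported: no rule censors OS at progression, and nothing shows how sites acted.

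**Conclusion.** The inconsistency is real and worth correcting, but its effect is conditional. Bias requires both that some sites applied the narrow text and that the death hazard is higher after progression. The second is plausible but not quantified in the documents. If either fails, OS is unbiased on this account.

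Under the assumed inputs, 12-month OS is overstated by about 0.3 to 1.4 points if a quarter of subjects are affected and 0.6 to 2.9 if half are. Confidence in the textual conflict is high; confidence in any actual bias is not.

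A reader might extend the calculation to loss of every progressor or to 24-month OS, where the figures would be larger. The documents do not support either extension. Total loss would need every site to disregard the inclusive sections and both footnotes. Full 24-month follow-up at 30 April 2018 would need a first dose by 30 April 2016, 66 days after the original protocol date of 24 February 2016, and SAP Table 1 lists no later efficacy cutoff.

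**What to change.** 1. **Wording.** Reconcile 5.4.1 and 6.1.1.1 with 5.1, 5.3.1.1 and the two footnotes. In 5.4.1, state that survival status is collected every 6 months for 2 years after venetoclax stops, whether or not progression has occurred, unless consent is withdrawn. In 6.1.1.1, state that recording progression does not end participation in survival follow-up. Clarify the call sentence under Disease Assessments to match.
2. **OS table.** Add one line: the number of subjects with progression and no recorded death who stopped venetoclax more than about 6 months before the cutoff, so that a first call was due, but have no contact after the 30-Day Safety Visit.
3. **Conditional retrieval.** Only if that number is material, retrieve vital status for those subjects where consent and local rules allow. The protocol synopsis is dated October 2020, so many 2-year windows may have closed and new wording alone would not repair existing data.

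The cost is a short text change, a note to sites and one table line. No new assessment is created, since the calls are already scheduled in both appendices. If step 3 is triggered there is some retrieval work, and it may be incomplete.
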